**TITLE**

Cranio-spinal Neurosurgical Approaches: Qualitative and Quantitative Analysis and Validation of New Minimally Invasive Techniques on Cadaveric Anatomical Models.

Acronym: **Neuro_SURGEM** (Neurosurgical Simulation and Quantitative Evaluation Methods)

Promoter: **Fondazione Policlinico Universitario Agostino Gemelli, Rome, Italy**

Date: **16/04/2025**

ABSTRACT

In recent years, the preclinical phase has become crucial for surgical research, as highlighted in the IDEAL framework (Idea, Development, Exploration, Assessment, Long-term study), which underscores the need for rigorous evaluation in the development of new surgical techniques (1-3). Our research focuses on the systematic analysis of different crano-spinal surgical approaches, using an innovative quantification system (BrainChop software). This preclinical study is conducted at the "SURGEM" anatomical laboratory at the Catholic University of the Sacred Heart in Rome. The study spans 36 months and includes several stages of cadaveric dissection with the aim of obtaining:

1. Quantification methods of working volumes and exposed area;
2. Analysis of anatomical variants;
3. Anatomical simulations;
4. Validation of new instruments/techniques.

The goal of this study is to deepen, through laboratory simulations, cranial (craniotomy, macro and minimally invasive) and spinal approaches with particular emphasis on the quantification of working volume and exposed area, anatomical variant analysis, and validation of new techniques/instruments (14-24). Using anatomical specimens and a neuronavigation system, various surgical techniques will be simulated with different types of dedicated instruments. This study will also analyze vascular, nerve, and bone anatomical variants that may influence surgical outcomes and intraoperative management of anatomical anomalies. Tumor resections will be simulated, with the goal of analyzing in detail the surgical access trajectories and resection areas.

35 Anatomical specimens will be used, including the voluntary donation program of the Agostino Gemelli University Hospital IRCCS - Catholic University of the Sacred Heart, in compliance with Italian law. Dissections will be performed using neurosurgical instruments, and data will be cataloged and anonymized, with proper storage. This research aims to improve the understanding and effectiveness of crano-spinal surgical approaches, promoting continuous innovation in surgical techniques. At the end of the three-year project, we expect not only to provide a detailed and quantitative analysis but also to make a significant contribution to the scientific literature in surgery and neurosurgery.

INTRODUCTION

BACKGROUND

In recent years, the preclinical phase of research in surgery has been recognized as a critical moment for the development of new techniques and surgical approaches. The IDEAL framework (Idea, Development, Exploration, Assessment, Long-term study) represents a reference model for describing the various phases of surgical research, highlighting the importance of preclinical evaluation both in the development and validation of new surgical approaches (1-3).

In Italy, the Law Number. 10 of February 10, 2020, introduced specific regulations concerning the donation of one's body and tissues post-mortem for study, training, and scientific research purposes, limited to those who have given their consent during their lifetime. The use of the human body or post-mortem tissues is governed by the principles of solidarity and proportionality, and regulated in a way that ensures respect for the dignity of the human body. This law has enabled the Fondazione Policlinico Universitario Agostino Gemelli to expand its study, training, and research activities, including the possibility of accepting body and tissue donations from individuals who have consented during their lifetime, thus contributing to the advancement of medicine and biotechnology.

The anatomical laboratory provides a controlled environment, ideal for simulating surgical procedures, allowing the analysis of multiple variables that influence the effectiveness of the procedure and cannot be controlled in clinical practice (4–14). Recently, the Principal Investigator (PI) developed, in collaboration with the University of Toronto, a navigation system that allows for the quantification of the workspace to define a specific surgical approach (14–19). This new method has been used in several anatomy laboratories, including those at the Universities of Brescia, Toronto, and Geneva, to conduct comparative quantitative studies on various neurosurgical, otolaryngological, and skull base surgery approaches. Some of the results obtained have been published in international scientific journals (14–24).

Objective

The main objective of this study is to conduct a preclinical and systematic analysis of the various cranial and spinal surgical approaches to evaluate their potential and limitations in an objective manner. Attention will be particularly focused on the study of skull base approaches, spinal approaches, quantitative studies, exploration of anatomical variations, and the validation of new surgical approaches and related instruments.

Endpoints

Primary Endpoints:

1. Quantification of Work Volume and Exposed Area in Crano-Spinal Surgical Approaches

Work volume represents the three-dimensional operative space created by each crano-spinal surgical approach. Quantification will be performed using BrainChop imaging software on standardized CT scans. Segmentation will follow predefined protocols to ensure reproducibility. Higher values indicate a larger and more accessible operative corridor. Exposed area corresponds to the two-dimensional anatomical surface revealed by each surgical approach. Measurements will be obtained from CT-based reconstructions using the same standardized segmentation workflow. Higher surface values reflect wider surgical exposure.

Unit of Measure: cubic millimeters (mm³) and square millimeter.

Time Frame: Measurements will be obtained twice with BrainChop software for each approach on every specimen: before the dissection using baseline CT imaging and after completing the approach using repeat CT imaging on the same day.

Secondary Endpoints:

1. Analysis of anatomical variations influencing surgical approaches.
2. Validation of new surgical instruments and techniques on cadaveric specimens.
3. Average operative time for each surgical approach: Determining the average time required to complete each type of surgery (macrosurgical, microsurgical) based on the adopted surgical approach. The analysis will focus on the duration of the intervention for each approach, comparing the relative efficiency of the techniques.
4. Assessment of the perceived difficulty by surgeons during the execution of surgical approaches: Collecting subjective evaluations on the difficulty of the procedure using a difficulty rating scale (e.g., Likert scale), considering factors such as familiarity with the technique, the anatomical complexity of the cadaver, and the ergonomics of the instruments used.
5. Assessment of the visibility of target anatomical structures through different visualization methods: Measuring the visibility of areas of anatomical interest using different visualization methods (macrosurgical, microsurgical). This endpoint will focus on the effectiveness of the different modes in providing clear visibility of critical anatomical structures during the surgical procedure.
6. Acceptability and feedback from surgeons on the use of new surgical techniques and instruments: Gathering feedback from participating surgeons on the new instruments and surgical techniques, evaluating their experience in terms of comfort, ergonomics, ease of use, and ease of learning the techniques employed during the simulation.
7. Effectiveness of dissection and surgical training courses: Measuring the effectiveness of dissection and hands-on training courses using cadaveric specimens, through pre- and post-training tests. This endpoint will focus on the improvement of participants' technical skills, with particular attention to their ability to apply the new surgical techniques learned during the simulations.

Methodology

Study Design

This study is a monocentric, observational, non-profit study that will be conducted on cadaveric anatomical specimens. No drugs or medical devices will be used on human subjects. The study will have a duration of 36 months and will begin after approval from the ethics committee.

The study will be divided into three distinct phases:

- **First and Second Year:** The main objective will be the quantitative analysis of the different surgical approaches. This will be accomplished using the innovative research method already applied by the Principal Investigator (PI) for the preclinical study of skull base surgical approaches.
- **Third Year:** The focus will be on macroscopically and microscopically visualized skull base and spinal approaches. Quantitative analyses will be conducted, relevant anatomical variations will be explored, and new surgical approaches and related instruments will be validated.

Setting

The anatomical dissections will be performed at the SURGEM Laboratory (located in the Settorian Room of the Institute of Pathological Anatomy at the Catholic University of the Sacred Heart in Rome). Recruitment of specimens began on 15/10/2025 and will continue throughout the study, which is expected to last for three years. The dissections, data collection, and analysis will be carried out continuously during this period.

Procedure

The anatomical specimens will be sourced from the Catholic University of the Sacred Heart's voluntary donation program and the Science Care Program. Sixty percent of the specimens will undergo specific preparations, including arterial and/or venous injections with silicone, consisting of a base and catalyst (Xiameter®, Midland, MI, USA) and colored with Pintasol® (Mixol® Red E-L3mix, Kirchheim unter Teck, Germany). The specimens will undergo high-resolution CT scans, and the DICOM images will be imported into a dedicated neuronavigation system (GTx-Eyes II Approach Viewer, University Health Network, University of Toronto, Toronto, Ontario, Canada). In some cases, CT scans will be repeated after dissection, and new calculations will be made using the neuronavigation software.

CT scans will be performed at the Institute of Forensic Medicine at the Catholic University of the Sacred Heart. The source of the specimens will be tracked and recorded, including:

- Voluntary donation program at the Catholic University of the Sacred Heart, Rome, Italy, in accordance with Italian law (LAW 10 February 2020, No. 10 and DECREE OF THE PRESIDENT OF THE REPUBLIC 10 February 2023, No. 47);
- Science Care, USA.

The dissections will be performed using neuro-surgical instruments specific for skull base surgery available at the SURGEM laboratory:

- Complete set of Rhoton dissectors (Rhodon Micro Dissector).
- Complete set for skull base surgery (Karl Storz®, Germany).

- Zeiss microscope (UCSC 119473).

The specimens will be cataloged according to their source, and anonymized data provided by the donor centers will be entered into a database. Proper storage of the specimens will take place at the Institute of Pathological Anatomy (Head: [name]) at the Catholic University of the Sacred Heart. Non-fixed specimens will be stored frozen at -20°C in dedicated freezers, while fixed specimens (with formalin) will be stored at 4°C in a solution (formaldehyde, glycerol, alcohol reagent, and water).

Variables

The approaches will be performed in a modular manner, from the least invasive to the most extensive. Various surgical approaches will be simulated using surgical instruments dedicated to skull base surgery, spinal surgery, and in both macrosurgical and microsurgical visualization modes.

The quantification of the working volume and the exposed area for each surgical approach will be calculated with an open-source software (BrainChop) on the CT scans of the specimens obtained before and after surgical dissection. For each specimen's CT scan, the area of interest exposed by the different approaches to be compared will be outlined using the BrainChop software (14-24).

Error and Control

To minimize potential sources of error, rigorous control methodologies will be implemented during data collection. Each analysis will be repeated multiple times to ensure the accuracy of the results.

Sample Definition

Given the descriptive nature of the study, a formal sample size determination is not required. However, we estimate that 35 cadavers will be enrolled over the three-year period.

Statistical Analysis

Quantitative variables will be summarized as means and standard deviations, while qualitative variables will be reported as absolute and relative frequencies (percentages). The effectiveness of the training will be evaluated by testing the mean difference of scores obtained in tests administered before and after the training, using the paired Student's t-test or the Wilcoxon test.

The difference in execution times between different techniques will be tested using ANOVA or the Kruskal-Wallis test. Linear models with random intercepts will be used to compare surgical volumes and exposed areas. A 95% confidence interval will be estimated using the bootstrap resampling method.

Results with $p < 0.05$ will be considered statistically significant. Statistical analysis will be performed using STATA software (StataCorp® LLC, College Station, TX, USA).

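### Macrosurgical and microsurgical operating times are to be compared and tested, but no rule says which specimen or side receives which mode, so this secondary contrast can be confounded with anatomy or specimen preparation

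*Protocol*

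**What the plan says.** Under Study Design the protocol describes itself so: "This study is a monocentric, observational, non-profit study that will be conducted on cadaveric anatomical specimens". Under Variables, approaches are to be simulated "in both macrosurgical and microsurgical visualization modes", and "The approaches will be performed in a modular manner, from the least invasive to the most extensive".

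Secondary endpoint 3 is the average operating time per approach, by macrosurgical or microsurgical type, with the stated purpose of comparing how efficient the techniques are. Statistical Analysis tests execution times between techniques by ANOVA or Kruskal-Wallis, with significance at p < 0.05. No pairing or specimen term is stated for that test.

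Secondary endpoint 4 lists "the anatomical complexity of the cadaver" among the factors in perceived difficulty. Under Procedure, 60% of specimens receive special preparation, including silicone injection of vessels. Specimens come from two sources, and they may be fixed or frozen. Background presents the laboratory as a controlled setting, "allowing the analysis of multiple variables that influence the effectiveness of the procedure and cannot be controlled in clinical practice".

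The primary endpoint is built differently: "Measurements will be obtained twice with BrainChop software for each approach on every specimen". Under Variables, "For each specimen's CT scan, the area of interest exposed by the different approaches to be compared will be outlined". Under Statistical Analysis, "Linear models with random intercepts will be used to compare surgical volumes and exposed areas".

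The protocol mentions no randomisation, counterbalancing or other assignment rule for modes, and it does not mention sides. Error and Control offers general control measures and repeated analyses.

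**The concern.** Observational fits poorly with techniques that the investigators themselves carry out and then compare. When the person who compares two techniques also chooses where each is applied, the choice can follow the anatomy. Here every specimen is scanned before dissection, so anatomy can be known before a mode is chosen. The protocol does not say that the scan would be used in this way.

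What is at stake is the time comparison between modes. If simpler heads, easier sides or better-prepared specimens go more often to one mode, that mode looks faster for reasons unrelated to the technique. More specimens make the wrong answer more precise without making it less wrong. Repeating the analysis does not help, and an analysis plan cannot restore an allocation that was not controlled at dissection.

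**Working it through.** **Which comparisons are exposed**

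- *Volume and exposed area (primary).* Each approach is measured on every specimen, the compared approaches are outlined on that specimen's CT, and the model has random intercepts. Anatomy is shared by the compared approaches and largely cancels. Not exposed.
- *Visibility (secondary 5).* An opened corridor can be viewed in both modes, so different specimens are not required.
- *Difficulty (secondary 4).* Statistical Analysis names no test between techniques.
- *New instruments (secondary 2 and 6).* The endpoints are validation and surgeon feedback. No standard-instrument comparator and no test are stated.
- *Operating time (secondary 3).* A comparison is promised and a test is named. Once an approach has been opened on a side, the time to complete it there cannot be measured again. The same approach timed in both modes therefore needs another side or another specimen. Exposed.

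**Size of the bias, illustration only**

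The protocol gives no effect size, SD, power or error rate, so there is no planned figure to reproduce. From the protocol: 35 specimens and the 0.05 level (two-sided assumed). All else is assumed: an 18 versus 17 split, no true difference between modes, correlation r of anatomical complexity with the chosen mode of 0.2 to 0.5, and correlation c of complexity with time of 0.3 to 0.7.

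For two nearly equal groups the groups differ in complexity by 2r SD, which shifts mean time by:

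spurious difference = 2 × r × c SD

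SE = √(1/17 + 1/18) = 0.338 SD, with 33 degrees of freedom. The rejection rate comes from the noncentral t distribution with noncentrality = difference / SE.

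| r | c | Spurious difference (SD) | Noncentrality | P(p < 0.05) |
|---|---|---|---|---|
| 0.2 | 0.3 | 0.12 | 0.35 | 6% |
| 0.3 | 0.55 | 0.33 | 0.98 | 16% |
| 0.5 | 0.7 | 0.70 | 2.07 | 52% |

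With r = 0, as expected under random allocation, the rate is 5%.

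**What pairing the sides gains**

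If all 35 specimens supplied both sides to one lateral contrast, with correlation ρ between sides:

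paired SE = √(2(1 − ρ)/35)

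- ρ = 0.3: 0.20 SD
- ρ = 0.5: 0.17 SD
- ρ = 0.7: 0.13 SD

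Treating 35 versus 35 sides as independent gives √(2/35) = 0.24 SD. The gain is an upper bound, because the 35 cadavers are spread over cranial and spinal approaches and some accesses are midline.

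**The case against.** The strongest reply is that the protocol never says the laboratory gives a specimen or side to one mode. The statement that both modes will be used may mean both on each specimen, and CT is described only for measurement and navigation. Secondary endpoint 3 may also speak of types of surgery rather than of two executions of one approach. This stands in part. A reader might infer that the investigators pick specimens by their scans, and the documents do not support that. What remains is that no rule exists and the team does the dissecting. Using both modes on each specimen would still leave open which side gets which mode when time is the outcome. If no approach is ever timed in both modes, the point falls away, and the protocol should then say so.

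A second reply is that the study calls itself descriptive and that adjustment may be left to a statistical analysis plan not shown here. The descriptive label is used to explain the lack of a sample size calculation, while the same protocol plans significance tests between techniques. A covariate or specimen term may well appear in an analysis plan, so the missing adjustment alone is not the criticism. Allocation has to be settled before dissection.

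A third reply is that the figures are wholly assumed and run from almost no inflation to severe inflation. That is correct. They show that the bias could matter, not that it will.

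A reader might also extend the point to the whole study, with easier anatomy passing for a better technique throughout. The documents do not support that: the primary endpoint is compared within specimen, visibility can be judged in both modes through one corridor, difficulty has no planned test, and no new-versus-standard instrument comparison is stated.

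**Conclusion.** The concern holds for one secondary contrast: operating time between macrosurgical and microsurgical execution of the same approach. The protocol promises this comparison and tests times at p < 0.05, but gives no rule for which specimen or side receives which mode, although such a contrast must use different sides or specimens. Confounding with anatomy or specimen preparation is therefore possible, and it does not shrink with sample size.

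Its size cannot be learned from the documents. The illustrative 6-52% false-positive rate rests on the assumed split and correlations. The conclusion itself needs only that some approach is timed in both modes and that assignment is left to free choice. This is a cheap improvement to a secondary comparison and does not invalidate the study.

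**What to change.** Where the same approach is timed in both modes:

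- **Lateral approaches:** assign the two modes to left and right of the same specimen by a random list opened only after the baseline CT.
- **Midline or single-access approaches:** randomise the specimen to the mode.
- **Analysis:** for the paired lateral contrasts, compare times within specimen, for example with the random-intercept model already planned for volumes and areas, in place of an independent-groups test.
- **Design label:** describe these contrasts as a randomised laboratory comparison.
- **Sequence:** the modular order from least to most extensive can stay.
- **Fallback:** where random assignment is not possible, report the time contrast as descriptive, without a p-value.

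The cost is a random list and a sentence or two in the protocol, with no extra specimens. Surgeons lose free choice of side or specimen, and specimens with only one usable side leave the paired contrast. The visualization-mode work is the focus of the third year, so the change can be made before most of it takes place.

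### Specimen preparation is not allocated or balanced over techniques, so comparisons across specimens, above all of operative time, can mistake preparation for a technique effect

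*Protocol*

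**What the plan says.** Under Sample Definition the protocol gives no formal sample size but states "we estimate that 35 cadavers will be enrolled over the three-year period". Under Procedure, "Sixty percent of the specimens will undergo specific preparations, including arterial and/or venous injections with silicone". The same section provides for two states of preservation: "Non-fixed specimens will be stored frozen at -20°C in dedicated freezers, while fixed specimens (with formalin) will be stored at 4°C". It gives no proportions for fixation and no rule for choosing the 60%.

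On records, Procedure says "The source of the specimens will be tracked and recorded, including" the university donation programme and a commercial programme, and later "The specimens will be cataloged according to their source, and anonymized data provided by the donor centers will be entered into a database". Source is the only catalogue key named. What the donor-centre data contain is not stated.

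The Endpoints section includes, as secondary endpoints, operative time compared between approaches, difficulty as perceived by the surgeon, visibility of target structures under macrosurgical and microsurgical modes, anatomical variants, and validation of new instruments and techniques. Under Statistical Analysis, "Linear models with random intercepts will be used to compare surgical volumes and exposed areas". Execution times are to be tested by ANOVA or Kruskal-Wallis, and qualitative variables are given as counts and percentages.

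**The concern.** Coloured silicone makes vessels easier to see, and formalin fixation alters how far tissue can be moved. Both plausibly affect visibility, difficulty and time. Preparation is a factor that the laboratory itself controls, yet the protocol does not link it to the technique, mode or instrument used on a specimen.

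If one technique happens to be performed more often on injected or non-fixed specimens, it may look faster or clearer for that reason alone. The named time tests have no specimen or preparation term to absorb this. The control offered under Error and Control, repeating each analysis, cannot remove an imbalance between specimens.

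A second, smaller matter is vascular variants. A variant that is harder to detect without injection may be missed in non-injected specimens. If all specimens then form the denominator, its frequency is understated.

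**Working it through.** The protocol has no power calculation to reproduce. Its inputs are 35 specimens and a 60% preparation share. Every effect size below is an assumption.

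**Numbers prepared.** 0.60 × 35 = 21 and 35 − 21 = 14. The 60% covers preparations that include injection, so injected specimens number at most 21 and non-injected at least 14. Arterial and venous injection taken separately may each have fewer than 21.

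**Operative time compared across specimens.** Take two techniques on separate specimens, 18 against 17, with no true difference. Let the outcome SD within a preparation type be 1, and let injection shift the outcome by d. The bias in the technique contrast is (difference in injected share) × d. The false-positive rate comes from 20,000 simulated t-tests at the 5% level (equivalent to a two-group ANOVA), with 21 injected in total each time.

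| Injected, technique A vs B | Difference in share | Bias, d = 0.5 | False positives, d = 0.5 | Bias, d = 1 | False positives, d = 1 |
|---|---|---|---|---|---|
| 11/18 vs 10/17 | 0.611 − 0.588 = 0.023 | 0.01 SD | 4.5% | 0.02 SD | 3.0% |
| 14/18 vs 7/17 | 0.778 − 0.412 = 0.366 | 0.18 SD | 7.4% | 0.37 SD | 13.2% |
| 18/18 vs 3/17 | 1 − 0.176 = 0.824 | 0.41 SD | 21.2% | 0.82 SD | 62.8% |

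In the balanced row the rate falls below 5% because preparation then only adds spread within each group. A preparation term would recover that lost precision.

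**Volume and area in the random-intercept model.** Take 35 specimens, 21 of them injected, with two measurements each, a preparation shift of 1, specimen SD 1 and residual SD 0.5, over 200 runs per design.

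- Both techniques on every specimen: mean bias about 0.01 SD, false positives 5%.
- One technique per specimen, chosen with probability 80% if injected and 20% if not: mean bias about 0.60 SD, false positives 37%.

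The second bias agrees with direct arithmetic. The share on the first technique is 0.6 × 0.8 + 0.4 × 0.2 = 0.56. The injected share is 0.48/0.56 = 0.857 on that technique and 0.12/0.44 = 0.273 on the other, a difference of 0.584. The random intercept therefore protects a comparison only where techniques are crossed within specimens.

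**Vascular variants.** Let p be the true prevalence and s the detection without injection relative to detection with it. If 21 of 35 are injected, detection there is complete and all 35 form the denominator, the observed frequency is p × (0.6 + 0.4s). For p = 20%:

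- s = 0: 0.20 × 0.60 = 12%
- s = 0.5: 0.20 × 0.80 = 16%
- s = 0.8: 0.20 × 0.92 = 18.4%
- s = 1: 20%

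The protocol gives no value of s. The result runs from no loss to a 40% relative loss, and the low end would be lower if fewer than 21 are injected.

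**The case against.** The strongest defence is that the primary endpoint is largely safe. The Endpoints section has volume and area measured for each approach on every specimen. The Variables section has approaches done in modular order and those being compared outlined on each specimen's CT. With a random intercept, a specimen-level preparation effect then nearly cancels. This stands, and a reader should not infer that the volume and area comparisons are confounded as planned.

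A reader might also infer that source is the only thing recorded. The text does not say so. Donor-centre data of unstated content also enter the database, and fixed and non-fixed specimens are stored differently, so the laboratory must know fixation status. Source is the only key named, and no more than that can be claimed.

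A third tempting reading is that vascular frequencies are diluted. No sentence sets 35 as the denominator or codes an unassessable vessel as absent. Understatement is possible, not shown.

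It is also fair that the imbalances and shifts above are hypothetical, that nothing suggests technique will follow preparation, that the study calls itself descriptive, and that covariates and denominators may be left to a statistical analysis plan. What remains is allocation and data capture. No later analysis can adjust for a status that was not recorded, or repair a comparison in which technique and preparation coincide. The protocol also commits to significance tests of execution time and names tests without a preparation term.

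**Conclusion.** The point holds for comparisons made across specimens: operative time by the tests named, and visibility and perceived difficulty by the same reasoning. It reaches volume and area only if approaches are not crossed within specimens.

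With a shift of 0.5 to 1 SD and 18 against 17 specimens, the false-positive rate for time is about 7% to 13% under moderate imbalance and 21% to 63% under extreme imbalance. It is not inflated under balance. These figures rest on assumed shifts and shares, and they show what could happen rather than what will. The vascular range of 12% to 20% for a true 20% likewise depends on an unknown detection rate and on a pooled denominator that the protocol does not fix.

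This is a worthwhile low-cost improvement to the design. It does not show that the planned results would be wrong.

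**What to change.** - Record fixation and injection status for each specimen alongside source, and state how the 60% are chosen. Specimen recruitment is stated to have begun on 15/10/2025, so this is best done early.
- Compare techniques, modes and instruments within specimen where possible. Otherwise, balance preparation over the compared groups with an allocation list, using coarse factors such as injected yes/no and fixed yes/no.
- Replace the plain execution-time test with a model that has a specimen random intercept (useful where a specimen yields more than one time) and a coarse preparation term. The term does not replace balance. At 18/18 against 3/17, the adjusted contrast would rest on 18 against 3 injected specimens, with variance (1/18 + 1/3)/(1/18 + 1/17) = 0.389/0.114 ≈ 3.4 times that of the full 18 against 17.
- Report arterial and venous variant frequencies among specimens with the matching injection, in addition to any pooled figure.

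**Cost.** The changes need an allocation list and two database fields, and no extra specimens. Coarse coding uses about two degrees of freedom and makes four cells, about 35/4 ≈ 9 specimens each. Full coding (two fixation levels, four injection levels) uses 1 + 3 = 4 and makes eight cells of about 35/8 ≈ 4, too thin to balance well over many approaches. The vascular denominator falls to at most 21.
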